# 4. Research Procedures:

- a. In the space below, describe in detail the research procedures (do not use an attachment):
  - Screening and Baseline assessment: Upon the consent, participants will be screened for their eligibility in addition to the criteria. We will use Mini Mental State Exam (MMSE; 3.Appendix 1) and TMS safety-screening questionnaire (3.Appendix 2) to ensure that participants do not have any cognitive impairments or contraindications for TMS. In addition, they will be asked to perform a 10 meter walk test to ensure they are able to walk 10m independently.

Once the eligibility is determined, each participant will be assessed with the Fugl-Meyer Motor Assessement (FMA; 3.Appendix 3) scale to quantify their motor impairment and a Trail-Making Test (TMT; 3.Appendix 4) to assess their executive function.

2. **Assessements**: Each participant will be tested with a gait assessment, followed by a counting task performance and a neurophysiological assessement.

2a. Gait Assessment: The gait assessment consists of walking at self-selected speed on the GaitRite carpet walkway. Gait performance (time taken, gait speed, stride cycle, step length) will be recorded by the GaitRite. The assessment will be repeated 3 times with about a 1 minute break between trials.

The walking test will then be repeated for another 3 trials under a dual-task condition in which the participants will perform the walking task in conjunction with a counting task. Before the 'Go' command, the tester will verbally provide a random number ranged from 30 to 100. They are then asked to perform the TUG test and count backward by 3 from the given number (e.g. 87, 84, 81, ...). During the dual-task TUG test, the participants will be asked to priortize the counting task.

In addition to the GaitRite measurement, the gait assessment will be videorecorded such that participants' performance on the counting task can be quantified offline (number of correct responses).

2b.Counting Task assessment: After the participants finish the gait assessment, the counting task will be repeated 3 times while they are seated.

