During each visit, they will receive 5Hz rTMS delivered to the target area (hot spot of the right tibialis anterior at the M1, left SMA, or left DLPFC). The 5Hz rTMS will be delivered in the form of 24 10-second trains with a 30second intertrain interval (a total of 1200 pulses) via a airfilled figure of 8 coil (Figure 2). The stimulation intensity will be set at 90% of individual RMT. We have previously shown that this protocol was effective to upregulate corticospinal excitability.

Figure 2. Air-filled coil for rTMS

After the rTMS protocol, corticospinal excitability will be reassessed using single pulse TMS again (procedure 2c). Participants will then perform the gait assessment (procedure 2a) and the counting task (procedure 2b).

Each participant will be tested for 3 visits (each visit will be 7±2days apart between two successive visits). Each visit will start with the assessment and be followed by a rTMS protocol. The target area for the rTMS protocols varies across visits (e.g. visit 1: Left SMA, visit 2: Left M1, and visit 3: Left DLPFC). The order will be pseudo-randomized and counterbalanced within each group.

4. Outcomes and data analysis: The primary outcome of this project is participant performance on the TUG test under single and dual-task conditions. The time taken to complete the TUG test under the two conditions will be used to derive dual-task cost (TUGdual – TUGsingle/TUGsingle). The dual-task cost will be compared across three rTMS protocols using repeated measure ANOVA. The secondary outcomes of the projects include gait parameters obtained from the

The secondary outcomes of the projects include gait parameters obtained from the GaitRite, MEPs measured under procedure 2c. These measures will be analyzed using repeated measure ANOVA as well.

b.	Is video recording a part of the s	tudy?	🛛 Yes 🗌 No	
	With sound $\square$	Without sound		
C.	Is audio recording a part of the s	tudv?		Yes 🗆 No

*If you answered "yes" to question #4b or 4c, describe the purpose of the recording and who will have access to these recordings.* 

The video recording will be used to quantify the number of corrected responses participants made on the counting task.

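### Single-task walks always precede dual-task walks, so fading of a site's rTMS effect between the two blocks enters the primary dual-task cost and does not cancel across sites

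*Combined protocol and SAP*

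**What the plan says.** All references are to section 4 (Research Procedures) of the combined protocol and SAP.

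- **Order within a gait assessment (procedure 2a).** The single-task walk comes first: "The assessment will be repeated 3 times with about a 1 minute break between trials". Next: "The walking test will then be repeated for another 3 trials under a dual-task condition". The break between the two blocks is not stated.
- **When the assessment is done.** It is done before stimulation ("Each visit will start with the assessment and be followed by a rTMS protocol") and again after it. The post-rTMS run follows the single-pulse excitability reassessment and points back to the same procedure, so the order is the same.
- **What is counterbalanced (item 3).** "The order will be pseudo-randomized and counterbalanced within each group". This refers to the order of the target areas over the three visits. Nothing alternates or randomises single-task and dual-task trials.
- **Primary endpoint (item 4).** "The time taken to complete the TUG test under the two conditions will be used to derive dual-task cost".
- **Primary comparison (item 4).** "The dual-task cost will be compared across three rTMS protocols using repeated measure ANOVA". The plan does not say whether the pre-rTMS value enters this analysis.

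**The concern.** Dual-task cost is the second block's time relative to the first block's time. With a fixed order, everything that changes between the blocks is carried by the task contrast: warm-up, fatigue, and minutes since the last train.

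Most of that is harmless for the research question, which compares sites within the same participants, because every visit uses the same order. Fading of the stimulation effect is different. It exists only after stimulation, and its size depends on how much the site did. If a site speeds walking in both tasks and the effect is wearing off, the single-task block gets the larger share of the gain and the dual-task block the smaller share. The ratio rises although the true cost has not changed. A site with no effect shows no such rise.

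The general speed-up behind this artefact is plausible here. One target is the leg area of M1, and section 1 motivates SMA by its association with gait recovery. The same section reports that DLPFC stimulation improved dual-task cost with little effect on gait. The artefact could therefore fall unevenly on the three sites being compared.

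**Working it through.** The documents state no drift, decay rate, effect size or SD, so there is no planned figure to reproduce. The endpoint is read as (dual − single)/single, because the printed brackets are incomplete, with the same walking test in both blocks.

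**Assumed inputs (none from the documents).** True cost c = 0.30 to 0.50. Fractional gain g = 5-15%, equal in both tasks, at the single-task block. Half-life h = 10 to 30 min. About 4 min between block midpoints: 15 s trials with 1 min breaks give 3.75 min, and a 5 min rest between blocks would give 7.75 min. The fraction of effect left at the dual-task block is r = 0.5^(gap/h).

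**1. Drift common to all sites.** If dual-task time is multiplied by (1+d) at every visit, each cost shifts in level by about (1+c)d, but the difference between two sites is only multiplied by (1+d). Take 15 s single and 20 s dual (cost 33.3%), and compare a site with 5% single-task and 10% dual-task gain against a null site. The true contrast is −7.0 points. With d = −5%, +5% and +10% it becomes −6.7, −7.4 and −7.7. The sign does not change.

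**2. Site-specific fading, equal gain in both tasks (true change in cost zero).**
Shift = (1+c) × g(1−r)/(1−g).
- Low end (g = 0.05, h = 30, c = 0.30): r = 0.5^(4/30) = 0.912, and 1.30 × 0.05 × 0.088/0.95 = 0.006, or +0.6 points.
- High end (g = 0.15, h = 10, c = 0.50): r = 0.5^(4/10) = 0.758, and 1.50 × 0.15 × 0.242/0.85 = 0.064, or +6.4 points.
- A site with g = 0 shows 0.

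**3. Unequal gains.** With single-task gain e_s and dual-task gain e_d, the observed change is (1+c) × [(1 − e_d·r)/(1 − e_s) − 1]. It becomes positive, hiding a true benefit, only if r < e_s/e_d. At cost 33.3%, a 4 min gap and a 10 min half-life (r = 0.758):

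| e_s | e_d | True change (points) | Observed (points) | Half-life needed for reversal |
|---|---|---|---|---|
| 0% | 10% | −13.3 | −10.1 | never |
| 5% | 10% | −7.0 | −3.6 | below 4 min |
| 8% | 10% | −2.9 | +0.6 | below about 12 min |

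The last column is 4/log2(e_d/e_s). An 8 min gap raises the last two thresholds to 8 min and about 25 min.

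**4. Effect of interleaving.** In the planned order, single-task trials are at positions 1, 2, 3 (mean 2.0) and dual-task trials at 4, 5, 6 (mean 5.0), a gap of 3 slots. In single-dual-dual-single-single-dual they are at 1, 4, 5 (mean 3.33) and 2, 3, 6 (mean 3.67), a gap of 0.33 slot. Modelling the six trials one by one, 4/3 min apart and with g set at the first trial, the shift in step 2 runs from 0.58 to 5.77 points in the planned order and from 0.07 to 0.65 in the interleaved order, about one ninth as large.

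**The case against.** A reader might infer that any drift between blocks biases the site comparison. It does not. The design is within participant, with the same order at each visit, so common warm-up, practice or fatigue moves all three sites together. A 3% drift at a 40% cost shifts each cost by 1.40 × 0.03 = 4.2 points. That is a shift in level; on a 7-point contrast it changes the difference by about 0.2 points.

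A reader might also infer that the order will make the best site look worst. The documents do not support that. Reversal needs nearly equal gains in both tasks and fast fading. What section 1 says of DLPFC is the case of little single-task gain, where reversal cannot occur or needs extreme decay. Where gains are equal, the site has no true benefit on this endpoint to reverse.

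The upper end is also demanding. Gait testing follows the excitability reassessment and, per section 6b, takes place in another lab. If that delay is 10-15 min (an assumption), a 15% gain remaining at a 10 min half-life implies 30-42% at the outset. At a 30 min half-life the range is only 0.6 to 2.3 points.

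Finally, interleaving adds switching between plain walking and counting, and section 1 links DLPFC to task switching.

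All of this limits the size and certainty of the bias. It does not remove it. Rest does not stop fading, and a longer rest between blocks widens the gap. A pre-rTMS assessment in the same order cannot correct for something that exists only after stimulation. The switching objection is a small cost to be named, softened by the roughly 1-minute breaks.

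**Conclusion.** The concern holds in a limited form. Task condition is confounded with time since stimulation in the primary endpoint, and site-specific fading of the rTMS effect is the part that does not cancel across sites. For a site that speeds walking generally, the overstatement of cost is about 0.6 to 6.4 percentage points under the assumed gain, half-life, gap and true cost. For an effect specific to dual-tasking, the result is dilution. Reversal is conditional on the remaining fraction falling below the ratio of single-task to dual-task gain, for example 8% against 10% with a half-life under about 12 min.

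Since the documents give no decay rate and no SD, the actual size cannot be fixed, and whether it would matter against the noise in a 10-person pilot cannot be shown. The case for change rests on the bias being avoidable at almost no cost.

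**What to change.** In procedure 2a, run the same six trials interleaved in one fixed order, for example single-dual-dual-single-single-dual. Use that order at every assessment, before and after rTMS and at all three visits. State that the break of about 1 minute applies between all six trials. Compute dual-task cost from these trials as planned.

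Two additions would help in reading the result: record the time since the last train for each trial, and report single-task and dual-task times beside the cost.

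When editing this text, reconcile procedure 2a with item 4. Procedure 2a describes walkway trials in the single-task block but names the TUG in the dual-task block, while item 4 needs the TUG in both.

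**Cost:** a reordered trial sheet, with no extra trials or visits. The tester must restate the instruction before each trial. Some task-switching carry-over is possible, and keeping the break between all trials limits it.

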# 2. Participant Information:

a. Description of participants in study:

Ten men and women with a diagnosis of left hemisphere stroke and age >18 years will be recruited to participate in this pilot project.

- b. Approximate number of participants: 10
- c. Vulnerable populations as participants (check all that apply):

Prisoners[	
Pregnant women	
Fetuses / neonates	
Minors	

NOTE: Researchers must comply with the federal mandate to report child abuse. See instructions for details.

d. Age (or age range) of participants: > 18 years

Provide the rationale for inclusion/exclusion on the basis of age:

- 1. This study will not include individuals age below 18 years for a few reasons. Stroke is relatively uncommon in persons younger than 18 years. Further, rTMS safety data in children and adolescents are less well-established. We exclude individuals younger than 18 years for both scientific merit and safety concern.
- e. Sex of participants ...... Both

Provide the rationale for inclusion/exclusion on the basis of sex:

If yes, provide a description of the exclusion criteria and the rationale for using these criteria:

g. List and provide rationale for any other inclusion/exclusion criteria:

Inclusion criteria:

- Age above 18 years
  Stroke is very unlikely in individuals age below 18 years. Further, there are limited data to support the safety of rTMS in individuals younger than 18 years.
  - Diagnosis of Left hemispheric stroke at least 6 months ago
    Left dorsolateral prefrontal cortex has been shown to play an important role in human dual-task performance. We therefore specifically target those with left hemispheric lesion since they demonstrate greater deficits in dual-tasking. We exclude acute and subacute (< 6 months) stroke because spontaneous recovery is very likely to occur

during acute and subacute phases. This will lead to difficulty in result interpretation with the current single group design.

- First time stroke OR complete gait recovery from prior stroke
  Individuals with more than one stroke often have more than one lesion location or involve more than one hemisphere. This would potentially complicate the rTMS application. We therefore exclude those with multiple strokes such that our sample can be more homogenous.
- 4. Able to walk independently for at least 10 meters with or without walking aids 2.Participants are required to walk independently for the behavioral testing.

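### Random starts from 30 to 100 let the length of the counting task vary by chance from 10 to 33 responses, with no matching and no rule for reaching zero

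*Combined protocol and SAP*

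**What the plan says.** Section 4 (Research Procedures), item 2a, first has participants walk three times without a second task. Then: "The walking test will then be repeated for another 3 trials under a dual-task condition". Before each of these trials "the tester will verbally provide a random number ranged from 30 to 100", and the participant must "count backward by 3 from the given number (e.g. 87, 84, 81" and so on. In this condition "the participants will be asked to priortize the counting task". The walk is filmed so that "participants' performance on the counting task can be quantified offline (number of correct responses"). Item 2b repeats the counting three times with the participant seated.

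The whole assessment is done before and after stimulation at each of three visits. Under item 4, Outcomes and data analysis, "The time taken to complete the TUG test under the two conditions will be used to derive dual-task cost", and that cost is compared across the three stimulation sites.

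The entry criterion on gait in Section 2 is "Able to walk independently for at least 10 meters with or without walking aids". It sets no minimum speed and no maximum time.

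The documents do not state:
- how the random number is generated;
- whether starts are matched between conditions, between pre and post, or between visits;
- what the tester does when the count reaches zero;
- the expected trial duration or counting rate.

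**The concern.** The counting task supplies the cognitive load that separates a dual-task trial from a single-task one. Its available length is fixed by the starting number, and that number is left to chance. A low start gives less than a third of the responses that a high start gives.

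If a participant reaches zero before the walk ends and stops counting, the last part of the walk carries no second task. Dual-task time would then tend to be shorter and the dual-task cost for that trial lower. If stimulation at one site made people count faster, sequences would end sooner after that site, and the effect could be mistaken for better dual-task gait. With 10 participants and three trials per condition, there is little averaging to absorb avoidable differences between trials.

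**Working it through.** The plan gives no figure of its own on this point, so there is none to reproduce.

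**Inputs from the documents** (Section 4, item 2a, and the visit schedule):
- Starts run from 30 to 100, which is 71 integers if both ends are included.
- The step is 3.
- There are three dual-task and three seated counting trials per assessment, two assessments per visit and three visits.

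**Assumptions** (not in the documents):
- The draw is uniform over the 71 integers.
- The response rate is 0.2 to 1.0 per second.
- The trial time is 20 to 60 seconds.

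**Step 1: responses available.** From start s, the number of subtractions that do not go below zero is floor(s/3).
- s = 30: 10
- s = 87 (the protocol's example): 29
- s = 100: 33

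Only 3 of 71 starts (30 to 32, 4.2%) give as few as 10.

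**Step 2: when a start runs out.** A trial runs out if rate × time > floor(s/3). From a start of 30, this takes 10/0.3 = 33 s, 10/0.5 = 20 s or 10/1.0 = 10 s.

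**Step 3: share of the 71 starts that run out before the trial ends.**

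| Responses per second | 20 s | 30 s | 40 s | 60 s |
|---|---|---|---|---|
| 0.2 | 0% | 0% | 0% | 8.5% |
| 0.3 | 0% | 0% | 8.5% | 33.8% |
| 0.5 | 0% | 21.1% | 42.3% | 84.5% |
| 1.0 | 42.3% | 84.5% | 100% | 100% |

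For example, 30 s at 0.5 per second needs 15 responses. Starts 30 to 44 fall short, and 15/71 = 21.1%.

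**Step 4: how much of the task is missing.** Reaching zero one response early is not the same as reaching it ten early, so average the shortfall over all 71 starts.
- 15 needed: shortfalls of 5, 4, 3, 2 and 1, three starts each, sum to 45. 45/(71 × 15) = 4.2%.
- 20 needed: shortfalls of 10 down to 1, three starts each, sum to 165. 165/(71 × 20) = 11.6%.

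**Step 5: a narrower range.** Counting trials per person are (3 + 3) × 2 × 3 = 36.
- 60 to 100 has 41 starts and allows 20 to 33 responses. It covers 36 trials without a forced repeat, and no start runs out if 20 or fewer responses are needed. If 30 were needed, starts 60 to 89 would still run out: 30/41 = 73%.
- 75 to 100 allows 25 to 33 responses but has only 26 starts, so at least 36 − 26 = 10 trials must reuse a start. If 30 were needed, 15/26 = 58% would still run out.

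**The case against.** The strongest reply is that the problem may never arise. Running out depends on counting rate multiplied by trial time, and the documents give neither. At 0.3 responses per second, a 30-second trial produces 9 responses and no start is exhausted. This stands, and it is why no single frequency can be quoted.

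A reader might infer that slower walkers will run out and finish the trial as single-task walking. The documents do not support that. Slow walking is not enough without fast counting. The protocol is also silent on what follows zero: the participant could continue into negative numbers or be given a new start. That silence leaves testers to improvise, which is a gap in standardisation, but it does not show that the load disappears.

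A reader might also infer that capped counts damage a named endpoint. The number of correct responses is scored from video but is not listed among the primary or secondary outcomes. Any effect on a named analysis would come through dual-task walking: the time behind the cost, and perhaps the GaitRite gait parameters.

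Finally, chance differences in starts add noise; they are not in themselves a systematic bias between sites. If no trial reaches zero, nothing here shows that the starting value matters.

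What survives is narrower. Available task length varies 10 to 33 by chance, starts are unmatched, no walking-speed limit keeps trials short, the instruction to put counting first encourages sustained counting, and the end of the sequence has no rule.

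**Conclusion.** The concern holds as a conditional one. In long trials with fast counting, a low start could be exhausted mid-walk; if counting then stops, the dual-task cost for that trial may be understated. It would be wrong to say that the cost is understated, because neither the running out nor the stopping is established.

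The size is uncertain. In a 30-second trial the affected share of starts moves from 0% to 21% to 85% as the assumed rate goes from 0.3 to 0.5 to 1.0 per second. Where 15 to 20 responses are needed, the average share of the task lost is modest, about 4% to 12%. All of these figures rest on a uniform draw and on assumed rates and times.

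This is a low-severity point. It is worth acting on because the task feeds the primary outcome and the change costs almost nothing.

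**What to change.** Make three changes to items 2a and 2b of Section 4:

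1. Raise the lower bound of the starting number, for example to a range of 60 to 100.
2. Replace the tester's ad hoc draw with pre-set lists that have the same average start at pre and post and at every visit, for both walking and seated counting.
3. Add one sentence saying what the tester does if the count reaches zero, and how such a trial is scored.

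If pilot trial times and counting rates are available, check the bound against them: the start should be at least 3 × the largest number of responses expected in a trial.

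The cost is a prepared list and a few lines of text, with no added visits, participants or analyses. There are two downsides. A narrower range means more overlap between number sequences, which may allow some practice effect. A trial needing more than 20 responses could still reach zero, so the rule in the third change is needed even with the higher bound.

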2c. Corticospinal excitability assessment: After the counting task assessment, participants will go through a series of corticospinal excitability assessement using single pulse transcranial magnetic stimulation (TMS, MagstimR Company, UK) . Surface electromyography (EMG) electrodes will be placed on the right Tibilias Anterior muscle with the participants seated on a reclining chair and wearing a pair of earplugs. EMG data will be sampled at 2000Hz and band-pass-filtered at 15-500Hz (Mega 600, Mega Electronics Ltd, Finland). The EMG data will be recorded and stored using MegaWin software (Mega Electronics Ltd, Finland) and analyzed offline using Matlab program (The Mathowroks, Inc, Natick MA). A Magstim 200 stimulator (Magstim Company, UK) will be used to deliver the TMS pulse via a double cone coil (Figure 1).

Figure 1. Double cone coil.

Neuronavigation system Brainsight TM (Rogue Research, Canada) will be used to reliably place the TMS coil over the scalp to precisely target the selected area. Stimulation will begin at 40% of maximum stimulator output and will be systematically increased to yield a motor evoked potential (MEP) from the tibialis anterior. A 'hot spot'of the right tibialis anterior will first to be determined. Hot spot is defined as the site at which the largest MEP is obtained at the lowest TMS stimulation intensity. Once the hot spot is determined, the resting motor thershold (RMT) will be defined. Resting motor threshold is the stimulation intensity that yield a MEP peak-to-peak amplitude > 50  $\mu$ V in 5 out of 10 consecutive trials. Once RMT is decided, the stimulation intensity

will be set at 120% RMT and 10 stimulations will be delivered to the hot-spot such that suprathreshold MEP can be recorded. These MEPs measures will be stored and analyzed offline to quantify corticospinal excitability.

3. **rTMS protocols:** After the corticospinal excitability assessment, participants will receive a high frequency rTMS applied to different areas at different visits.

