Headaches It has been shown that with repetitive stimulation on the scalp (in rTMS protocols), a small number of participants (< 28% cases) would develop transient headaches. The developed headaches usually resolved within 3-4 hours and respond well to over-the- counter pain medicine, such as 6.Tylenol.	To minimize this potential risk, we will exclude participants who are prone to develop headaches (e.g. history of migraine). We will use subthreshold intensity for rTMS protocols that will reduce the likelihood of developing headaches. In addition, the tester will stop the testing when they develop headaches during the test. 6.If participants do develop headaches and require pain medication, we will ask them to take the pain medication that has been approved by their primary care physicians.
RISK	STEPS TO MINIMIZE RISK
Changes in auditory threshold There is a risk of alteration in auditory threshold after TMS protocols as TMS produces loud click when it is charged. The changes in auditory threshold are transient (lasts about 1 day) and not different from going to a music concert.	To minimize the risk, we will provide earplugs during TMS testing.
RISK	STEPS TO MINIMIZE RISK
Seizure Risk of seizure is associated with high frequency rTMS and is higher in those who have history of seizure, on medication that are known to reduce seizure threshold. Risk of seizure is also higher when the rTMS parameters are set outside of the safety limits.	We will use a safety-screening questionnaire adapted from the recommendation of the international committee  . This questionnaire will help us to identify those at high risk of developing seizure and they will be excluded from participation. The rTMS protocols adopted in this project are within recommended safety limits  and we have previously conducted rTMS experiments using the same protocols without any adverse events  .

(Use continuation pages if necessary)

8. Will participants be told about the intent of the study prior to participating? ... X Yes No If "no," provide an explanation of why deception is necessary and the debriefing method to be used to fully inform the participants of the study's intent.

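### The motor threshold is measured with a double cone coil but sets the dose of a figure-of-8 coil, so rTMS intensity relative to the delivering coil's own threshold is unknown

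*Combined protocol and SAP*

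**What the plan says.** All of the dosing text is in section 4, Research Procedures, of the combined protocol and SAP.

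- **Threshold (item 2c).** "A Magstim 200 stimulator (Magstim Company, UK) will be used to deliver the TMS pulse via a double cone coil". With this equipment the tibialis anterior hot spot is found and RMT is set: "Resting motor threshold is the stimulation intensity that yield a MEP peak-to-peak amplitude > 50" µV in 5 of 10 consecutive trials. Ten MEPs are then recorded at 120% RMT.
- **Sequence (item 3).** "After the corticospinal excitability assessment, participants will receive a high frequency rTMS applied to different areas at different visits". Nothing is described between the two steps.
- **rTMS (item 3).** Stimulation is delivered "via a airfilled figure of 8 coil (Figure 2). The stimulation intensity will be set at 90% of individual RMT". The rTMS stimulator is not named. The protocol adds: "We have previously shown that this protocol was effective to upregulate corticospinal excitability".
- **Afterwards (item 3).** "After the rTMS protocol, corticospinal excitability will be reassessed using single pulse TMS again (procedure 2c"), which again means the double cone coil.

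The headache row of the risk table (section 7) relies on the intensity: "We will use subthreshold intensity for rTMS protocols that will reduce the likelihood of developing headaches". The same row also excludes headache-prone people and provides that "the tester will stop the testing when they develop headaches during the test".

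**The concern.** A threshold expressed in percent of stimulator output belongs to the coil and stimulator that produced it. Here one coil gives the threshold and another delivers the treatment, with nothing to link them. The output as written is 90% of the double cone RMT, whatever the relation between the coils. What cannot be stated is how that output compares with the figure-of-8 coil's own threshold.

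Two things depend on this. The first is the meaning of the reported dose. A null result, or a headache, could reflect a relative dose that nobody knows, and if the ratio between coils differs between people, a nominal 90% is a different relative dose in each. The second is the headache safeguard that rests on stimulation being below threshold.

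**Working it through.** **Inputs from the documents.** Double cone coil on a Magstim 200 for RMT (item 2c); figure-of-8 coil for rTMS at 90% of RMT (item 3); 24 trains of 10 s at 5 Hz, 1200 pulses (item 3); about 2.5 h per session and 7.5 h in total (section 5). No figure-of-8 threshold, conversion factor or rTMS stimulator model appears.

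**The plan's own figure.** 24 × 10 s × 5 Hz = 1200 pulses, which matches. The 90% is a specification and cannot be re-derived.

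**Dose relative to the delivering coil.** Let r = figure-of-8 RMT on the rTMS stimulator / double cone RMT on the Magstim 200, each in percent of maximum output. Output is 0.9 × double cone RMT, so as a share of the figure-of-8 RMT it is 90%/r. The range of r below is an assumption, chosen symmetric on the ratio scale (0.8 = 1/1.25).

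| r (assumed) | 90%/r | Relative to figure-of-8 threshold |
|---|---|---|
| 0.8 | 112.5% | above |
| 0.9 | 100% | at |
| 1.0 | 90% | below |
| 1.1 | 81.8% | below |
| 1.25 | 72% | below |

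The dose equals 90% only at r = 1 and is below threshold only for r > 0.9.

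**What re-measuring would do to the output.** It multiplies the setting by r. For an assumed double cone RMT of 40% of maximum output, the current rule gives 0.9 × 40 = 36%. With the delivering coil's threshold the setting is 0.9 × 40 × 0.8 = 28.8% at r = 0.8, or 0.9 × 40 × 1.25 = 45% at r = 1.25.

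**Cost of one more threshold per visit.** Assumed: 50 to 80 threshold pulses, 10 to 20 hot spot pulses, 5 s spacing, and 3 to 5 minutes of positioning.

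- Low: (50 + 10) × 5 s = 300 s = 5.0 min; plus 3 = 8.0 min; 8.0/150 = 5.3% of the session; 60/1200 = 5.0% of the rTMS pulse count.
- High: (80 + 20) × 5 s = 500 s = 8.3 min; plus 5 = 13.3 min; 13.3/150 = 8.9%; 100/1200 = 8.3%.
- Over three visits: 3 × 8.0 = 24 min to 3 × 13.3 = 40 min, out of 450.

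**The case against.** **The site comparison is not affected.** This stands. The research question concerns differences between loci, and the same coil and rule apply at every visit. A reader might infer that the mismatch biases the M1/SMA/DLPFC contrast; nothing in the documents supports that. Moreover, a tibialis anterior threshold is only a proxy for local dose at SMA and DLPFC with either coil, so the fix gives a locally meaningful 90% at M1 alone.

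**Participants are not shown to be overdosed.** Also right. A reader might infer that stimulation will be above threshold, that the headache statement is false, or that safety limits are breached. The documents give neither the size nor the direction of r, so none of these follows. Nor is a leg motor threshold shown to be a headache threshold.

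**The protocol has been used before.** Item 3 cites earlier efficacy, and the seizure row of the risk table says the same protocols ran without adverse events and lie within recommended limits. That is relevant reassurance on tolerability. It does not settle the dose question, because neither place says which coil set the threshold in that work.

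**It may be a gap in writing only.** The rTMS sentence names no coil for the RMT, and staff may already use the figure-of-8 coil. If so, one sentence closes the point. As written, the only RMT defined is the double cone one.

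**The remedy could raise exposure.** If r > 1, absolute output rises at all three sites. This objection stands, and the fix has to include a safety check.

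**Conclusion.** The point holds as a limit on how the dose is defined, and as a cheap improvement. As written, rTMS intensity is 90%/r of the delivering coil's threshold with r unknown: 112.5% to 72% over an assumed 0.8 to 1.25. The subthreshold statement is unverified; the other two headache measures do not depend on it. It is not a flaw in the primary comparison and not evidence of unsafe dosing.

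That the protocol sets RMT in procedure 2c only, with no step linking the coils, comes directly from the text. The size of any discrepancy rests wholly on the assumed range.

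**What to change.** **Change to section 4, item 3.**

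1. At each visit, after the pre-rTMS procedure 2c, measure tibialis anterior RMT with the figure-of-8 coil and the rTMS stimulator, and name that stimulator. Set rTMS at 90% of this value. Keep the double cone RMT for the 120% MEP measures.
2. Before delivery, confirm that the resulting setting is within the safety limits cited in the seizure row of the risk table.
3. If no figure-of-8 threshold is found at visit 1, use 90% of the double cone RMT at all three visits and report the dose as such.
4. If one is found at visit 1 but not at a later visit, carry forward the visit 1 rTMS output. Do not scale it up.
5. Record the output delivered and the threshold used at every session.

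If the figure-of-8 threshold is already taken in practice, writing that down is enough.

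**Cost.** Protocol wording plus, under the assumptions above, roughly 8 to 13 minutes and 60 to 100 single pulses per visit. The 2.5 h and 7.5 h figures in section 5 may need updating.

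**Downsides.** Added fatigue, which the risk table already lists; higher absolute output at all sites if r > 1; some participants dosed under the fallback, so not all on the same basis; and, since the coil used for the threshold in the earlier work is not stated, no way to tell whether the change moves toward or away from that dose.
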